The main data source for this study is surveys of intervention participants. Participants are surveyed at three different time points throughout the study. Two surveys (one nFORM and one local evaluation [OLLE] survey) are collected from participants at each of the first two waves of data collection. Wave 1 (nFORM entrance survey and OLLE pre-survey) of data collection happens during the program orientation session before the first primary workshop session, with make-ups administered as needed until three primary workshops have been received. Wave 2 (nFORM exit survey and OLLE post-survey) of data collection happens at or immediately after the final workshop session, with make-ups administered as needed for up to two weeks after primary workshops end. Wave 3 of data collection (the OLLE follow-up survey) happens one year after program enrollment.

Waves 1 and 2 of surveys are administered online using students' school computers, program tablets, or students' personal devices in the case of virtual cohorts. Paper surveys can be offered if necessary due to technological difficulties or facility restrictions. The link to complete the follow-up survey at Wave 3 is sent to participants via email, text message, and postcard/letter using a QR code. Participants can also complete the survey over the phone with evaluation team staff if they prefer.

Wave 1 of data collection began in June 2021 and will conclude at the end of March 2024. Wave 2 of data collection began in July 2021 and is expected to conclude in April 2024. Wave 3 of data collection began in June 2022 and is expected to conclude in March-April 2025.

The analyses for this study will use data from different survey waves, depending on the outcome. Short-term attitudinal changes will be assessed by comparing outcomes between Waves 1 and 2 (program entry to exit), and longer-term behavioral changes will be assessed by comparing outcomes between Waves 1 and 3 (program entry to follow-up).

A copy of the local evaluation survey codebook will be sent as a separate appendix to this plan.

Table 3. Sources of data to address the research questions

Data source	Timing of data collection	Mode of data collection	Start and end date of data collection
Intervention participants (nFORM entrance survey and OLLE pre-survey)	At the orientation session before the first primary workshop	In-person online survey or remote online survey	June 2021-March 2024

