Data source	Timing of data collection	Mode of data collection	Start and end date of data collection
Intervention participants (nFORM exit and OLLE post-survey)	At or immediately after the final primary workshop session with make-ups offered as needed	In-person online survey or remote online survey	August 2021-May 2024
Intervention participants (OLLE follow-up survey)	One year after program enrollment	Remote online survey sent via text, email, or QR code; phone survey	June 2022-March 2025

4. Outcome measures

The attitudinal research questions for this study will be answered by comparing post-survey responses collected at the end of primary workshop services to baseline survey responses collected before primary workshops begin. The behavioral research questions for this study will be answered by comparing follow-up survey responses collected one year after program enrollment to baseline survey responses collected before primary workshops begin. The one-year follow-up survey will be administered to all program participants who consent to be in the study and complete at least one baseline survey (nFORM or OLLE), regardless of program completion status or workshop delivery format. Because the post-surveys (nFORM exit and OLLE post-survey) are collected during or shortly after the final primary workshop, it is likely that only those complete the program will complete the post-surveys; however, all study participants who have consented and completed at least one baseline survey are eligible to take the post-surveys.

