For each outcome construct (healthy relationship attitudes, healthy relationship behaviors, healthy financial attitudes, and healthy financial behaviors), we have identified the relevant survey measures that are theoretically aligned with that construct. When analysis begins, we will generate a correlation matrix between items in a given construct to ensure that theoretically related items are also empirically related in our data set. Survey items will be reverse-coded as needed before checking for correlation strength. Items that are not strongly correlated with other items in a construct will be removed as necessary. Factor analysis will be used to ensure that all construct items hang together, using an alpha of 0.7 or higher as the acceptable threshold. If a constructed scale does not achieve an alpha of 0.7 or higher, even after removing items that are not well correlated, the outcome measure will be dropped from the analysis.

We will then create a composite measure for each construct by taking an average of the scores on each non-missing item in the construct. For these composite measures, we intend to use 20% as a threshold for allowable missing items; this plan is contingent on the final distribution of missing data in our data set. Participants who are missing more than 20% of items for a given construct will be assigned a missing value for that composite outcome measure. We will not be imputing truly missing values for outcomes. To create the construct score for each participant, the average of the relevant survey items will be divided by the number of non-missing values in the construct.

Table 4. Outcomes used to answer the research questions

Research question	Outcome name	Description of the outcome measure	Source of the measure	Timing of measure
RQ1	Healthy relationship attitudes	The outcome measure is a scale (value range 1-4) calculated as the average of nine survey items related to healthy relationship beliefs	nFORM entrance survey (A1.a-i); nFORM exit survey	Wave 1 (before primary workshops begin) and Wave 2 (at the final primary workshop)
RQ1	Healthy relationship attitudes	The outcome measure is a scale (value range 1-5) calculated as the average of three survey items related to expectations that youth have for their future relationship circumstances	nFORM entrance survey (A2.a-c); nFORM exit survey	Wave 1 (before primary workshops begin) and Wave 2 (at the final primary workshop)

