RQ2	Healthy relationship behaviors	The outcome measure is a scale (value range 1-4) calculated as the average of five survey items related to reported self-assessed skill with communication and conflict resolution	nFORM entrance survey (C1b.a-e); OLLE follow-up survey	Wave 1 (before primary workshops begin) and Wave 3 (one year after program enrollment)
RQ2	Healthy relationship behaviors	The outcome measure is a scale (value range 1-5) calculated as the average of six survey items related to the frequency of engaging in unhealthy conflict resolution behaviors	nFORM entrance survey (C3.a-f); OLLE follow-up survey	Wave 1 (before primary workshops begin) and Wave 3 (one year after program enrollment)
RQ3	Healthy financial attitudes	The outcome measure is a scale (value range 1-5) calculated as the average of seven survey items related to level of agreement with key financial attitudes	OLLE pre-survey (Q14.a-g); OLLE post-survey	Wave 1 (before primary workshops begin) and Wave 2 (at the final primary workshop)
RQ4	Healthy financial behaviors	The outcome measure is a scale (value range 1-5) calculated as the average of four survey items related to level of agreement with good money management habits	OLLE pre-survey (Q21.a-d); OLLE follow-up survey	Wave 1 (before primary workshops begin) and Wave 3 (one year after program enrollment)

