IVROP ReadyforLIFE Program Evaluation

Statistical Analysis Plan

August 29, 2024

ClinicalTrials.gov ID: NCT05244447

Analysis approach

The main goal of this descriptive study is to assess pre-post change scores in the means of the outcome constructs listed above among program participants before, immediately following, and one year after primary workshops. We will use paired sample t-tests to assess the magnitude and significance of mean score changes among program participants in the analytic sample for each outcome.

The analytic sample for each outcome construct consists of study participants who have a non-missing value at baseline and follow-up time points for that outcome (complete case). The analytic sample may vary by outcome construct based on prevalence of missing data at the baseline, post, or follow-up surveys for those questions. The final report will include descriptive statistics about the sample for each outcome, including which optional services (2.0, PLUS, or none) that participants received. As mentioned in the Outcomes section above, a respondent who answers some but not all survey items in a given outcome construct matrix will have their outcome value assigned as missing if they do not respond to at least 80% of the items in the construct. We will not impute missing baseline or outcome data for our analyses. Findings are considered statistically significant based on $p < 0.05$, two-tailed test. We will adjust our p-values for multiple hypothesis testing and report the adjusted p-values in the appendix of the final report.

As part of data preparation and cleaning, we will check for inconsistent and seemingly inaccurate data. The largest source of potentially inconsistent data that we anticipate is duplicate local evaluation surveys. Participants are able to, and occasionally do, retake the local evaluation surveys on Qualtrics. In the case of duplicate survey data, where participants have taken a local evaluation survey more than one time, we plan to take the following approach:

- Check for incorrectly entered Client IDs that inaccurately flag surveys as duplicates. Using the name and/or DOB fields on the local evaluation survey, we will check that responses that appear to be duplicates were in fact collected from the same participant multiple times (i.e., are true duplicates). If not, we will correct Client IDs as necessary.

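### Does the SAP need changing because its promised multiplicity adjustment names no method, family or deciding p-value?

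*SAP*

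**What the plan says.** The SAP (Analysis approach) plans one paired t-test per outcome. Its significance rule begins "Findings are considered statistically significant based on" and gives a two-tailed threshold of 0.05. The next sentence is the only one in either document on multiplicity: "We will adjust our p-values for multiple hypothesis testing and report the adjusted p-values in the appendix of the final report".

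Protocol section B.4, Table 4, lists six scales under four research questions. RQ1 and RQ2 have two scales each. RQ3 has one, "calculated as the average of seven survey items related to level of agreement with key financial attitudes", and RQ4 has one, "calculated as the average of four survey items related to level of agreement with good money management habits". A scale that fails the reliability threshold is dropped, so six is the most that will be tested. The SAP also repeats the analyses without 2.0 and PLUS participants, as a sensitivity check.

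On timing, the SAP is dated "August 29, 2024". Protocol section B.3 states: "Wave 2 of data collection began in July 2021 and is expected to conclude in April 2024". Table 3 gives the same wave as "August 2021-May 2024". Wave 3 was expected to run into March-April 2025.

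**The concern.** Two analysts could both follow the SAP and print different adjusted p-values. One might apply Holm to all six scales, while another applies it inside each research question. In the second case RQ3 and RQ4 have one scale each, so their p-values would not be adjusted at all. A third might use Benjamini-Hochberg, which controls a different error rate. Because the adjusted values go to an appendix, a reader may also suppose that the raw p decides what the main text calls significant.

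The dates sharpen the worry. RQ1 and RQ3 compare Waves 1 and 2, and on the protocol's calendar Wave 2 had closed before the SAP date. Both time points for three of the six scales would then have been in hand while the rule was still open. At stake would be the label on a small change, and a choice of rule that could follow the results.

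**Working it through.** **Inputs.** Six scales split 2/2/1/1 (protocol Table 4); two-tailed 0.05 (SAP, Analysis approach); 1,680 enrolled, 70% target response, 1,176 desired (protocol B.2); follow-up response above 80% (SAP, Attrition). The documents give no correlation between scales and no expected change. Correlations of 0 to 0.7 and changes of 0.05 to 0.15 SD are therefore assumptions. Clustering by class or school is ignored.

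**Step 1, the plan's own figure.** 1,680 × 0.70 = 1,176, which reproduces. At 80% response, 1,680 × 0.80 = 1,344. The documents state no power, effect size or study-wide error rate to check against.

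**Step 2, chance of at least one false finding, no true change on any scale, independent tests.**

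- Holm over six: 1 − (1 − 0.05/6)^6 = 4.9%
- Holm within each question: 1 − (1 − 0.025)^4 × (1 − 0.05)^2 = 1 − 0.9037 × 0.9025 = 18.4%
- Raw p: 1 − 0.95^6 = 26.5%

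**Step 3, dependence.** The same participants answer all the scales, so positive correlation is likely. With equicorrelated test statistics:

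| Rule | ρ = 0 | 0.3 | 0.5 | 0.7 | Bound, any dependence |
|---|---|---|---|---|---|
| Holm over six | 4.9% | 4.6% | 4.1% | 3.3% | 5% |
| Holm per question | 18.4% | 17.0% | 14.7% | 11.8% | 4 × 5% = 20% |
| Raw p | 26.5% | 24.1% | 20.7% | 16.4% | 6 × 5% = 30% |

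So 18.4% is the independence value for one choice of family. It is not a ceiling, and it falls under the positive correlations shown.

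**Step 4, would labels change?** Simulation gives the chance that at least one of the six scales is labelled differently by Holm over six, Benjamini-Hochberg over six and Holm per question. The same true change is put on every scale.

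| True change | n = 1,176 | n = 1,344 |
|---|---|---|
| 0.05 SD | 43–62% | 44–64% |
| 0.10 SD | 11–16% | 5–11% |
| 0.15 SD | at most about 0.2% | at most 0.1% |

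Three limits apply to this table.

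- Both n values come from the one-year response rate, so they concern RQ2 and RQ4. RQ1 and RQ3 use Wave 2, for which the documents give no n. Protocol B.4 expects mainly completers to answer that wave.
- The high figures count any one of six scales, at a change below what a single unadjusted test can detect with 80% power: (1.960 + 0.842)/√1,176 = 0.082 SD. For a single scale at n = 1,176, Holm over six and Holm per question disagree in about 14–16% of cases at 0.05 SD and 2.5–5.5% at 0.10 SD.
- The table matters only if the adjusted p decides. If raw p decides, method and family alter the appendix alone.

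**Step 5, timing.** The cover date falls after the scheduled end of Wave 2, but the protocol text speaks of the close of enrollment and of Waves 1 and 2 in spring 2024 as still to come. The wording therefore appears older than the cover date. Analysis is also described as future: "When analysis begins, we will generate a correlation matrix between items in a given construct". Data for RQ2 and RQ4 were not due to be complete until 2025. Nothing in the documents shows that anyone had looked at results.

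**The case for a change.** The best case for a change is that a promise to adjust cannot be audited without a method and a family. The study calls itself descriptive but still declares findings statistically significant, so the rule behind that label ought to be fixed. One sentence would do it, at no cost in data, and it would remove any suspicion that the rule was picked after the results were seen. The method matters too: with one family of six and two or three real effects, Benjamini-Hochberg gives a family-wise error of about 9.7%, against about 4.9% for Holm.

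The omission stands, and so does the arithmetic. The step from there to a needed change does not. The gap between 4.9% and 18.4% is the gap between controlling error across the study and controlling it per question. The protocol poses four separate questions and makes no joint claim, so the per-question family is not an error. Benjamini-Hochberg is likewise an accepted procedure that targets the false discovery rate. Asking the sponsor to write down any one of these would not correct a wrong result or bring in a better method. The raw-p reading is possible, but the adjusted values would still be published. With at most six tests, a reader who has the unadjusted p-values can apply any method or family by hand.

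**Conclusion.** No change to the plan is needed. This is missing detail that the analysts must supply anyway, since adjusted p-values cannot be computed without choosing a method and a family, and the report can name both beside the values. A sentence in the SAP before the final analysis, stating method, family and deciding p, would be harmless tidying and is optional.

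The choice moves the study-wide chance of a false finding between 4.9% and 18.4% if adjusted p decides by Holm, or to 26.5% if raw p decides. These figures assume six retained scales, independent tests and no true change anywhere. Labels are sensitive to the rule mainly for changes of 0.10 SD or less, and hardly at all at 0.15 SD. That last statement assumes adjusted p decides, the same true change on every scale, and the one-year n for all six, which is unsupported for RQ1 and RQ3.
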